## 11) Provisions to Monitor the Data to Ensure the Safety of Subjects\*

The Principal Investigator, [name], assumes responsibility for developing and implementing a data and safety monitoring plan to assure minimal risk and data integrity in this study. The plan assures that all data collected concur with all local, state and federal guidelines. The PI will work closely with his collaborators and will follow any data monitoring and safety requirements set forth by NIH.

The PI will examine accumulating data to assure protection of participants' safety while the study's scientific goals are being met and will conduct periodic reviews of accumulating safety and efficacy data. Along with his collaborators at the University of Miami Miller School of Medicine, he will determine whether there is support for continuation of the study, or evidence that study procedures should be changed, or if the study should be halted, for reasons relating to the safety of the study participants, the feasibility of the intervention under study, or inadequate study procedures (e.g., poor recruitment).

Procedures for the study will follow quality assurance (QA) procedures established by CLaRO for data management and safety, to ensure quality and consistency in the implementation of the protocol and data quality, to adhere to regulatory requirements and, most importantly, to protect the safety of study participants. The study will be monitored by the CLaRO Study Monitoring Unit, which is based at the School of Nursing and Health Studies. The Study Monitoring Unit will (1) verify compliance with regulatory requirements, (2) ensure that the PI and engaged study team members are fully informed of regulatory requirements and properly trained to perform the duties assigned, and (3) monitor procedures to prevent errors and minimize protocol deviations that can negatively affect quality of the data collected and compromise human subjects' protection. The project will have a quality assurance (QA) review: prior to initiation, upon conducting baseline procedures with the first wave of study participants; and bi-annually for interim reviews. For the initiation review the Study Monitoring team reviews protocol procedures and their manualization, documentation of staff training, evaluates that the study site is prepared to conduct the study, and ensures that the Regulatory Binder is complete. Interim monitoring visits will verify that study screening, consent, and data storage procedures are being conducted as stated in protocol. After each QA visit the Study Monitoring team prepares a written report that is sent to the study PI and to the CLaRO Executive Committee. These reports include deficiencies noted and plans for corrective action. The Study Monitoring team follows up with the study team to ensure that the corrective plan and any required reports to the IRB are filed in a timely manner. Protocol violations that are recurrent or

IRB Study Number: 20201202  
Version 4.02, Date: 11/10/2021

serious will be brought to the attention of the CLaRO Executive Committee for determinations regarding corrective action.

#### Adverse Event Reporting

In the event that an adverse event or otherwise untoward incident occurs as a direct result or in the context of the project, we will closely follow IRB directives and reporting policies. Specifically, we will report to the University of Miami IRB within 10 working days, in writing, all serious adverse or otherwise untoward events associated with procedures. To ensure monitoring of other study-related participant safety events or incidents, procedures regarding confidentiality and data integrity will be continually monitored and regularly audited.

In our experience, serious, unexpected adverse events related to study participation are rare. In addition, screening for adverse events potentially related to the study intervention will occur during the routine administration of study assessment measures. These interview-based indicators will augment required Serious Adverse Event (SAE) reports by the CHWs and study personnel, including specific items in the assessment interviews evaluating episodes of muscle or fall-related injuries, unexpected medical events, medical emergency room admissions, medical hospitalizations, or unplanned medical clinic visits. Should an adverse event occur, [name] (PI) will report it to the University of Miami Institutional Review Board (IRB) using the IRB SAE form. [name], in collaboration with co-investigators, will review the adverse event report and gather other information as needed to investigate it and determine the need for subsequent action. [name] will ensure that all adverse events are reported to the IRB in accordance with the University of Miami policies and in a timely manner. Any subsequent action will be documented and reported to the IRB.

*Identifying Events:* As noted, we will operationalize adverse/safety events for the study and protocols for their resolution. All interventionists and assessors will be trained on these protocols. Initially we will base these protocols on those developed for the HOLA pilot trial. For that trial, there were two categories of events: adverse events and safety alerts. These events may be identified during the baseline interview or the intervention period. Baseline adverse events are items that are identified and recorded by the interviewer during the baseline interview and are unrelated to the study or intervention. Adverse events are situations that occurred during the intervention period and are identified by the interventionist or by the interviewer during the 16-week assessment or any off-protocol interaction with a participant. All off-protocol contacts will be recorded. Adverse events occur anytime following randomization until study completion. Safety alerts are identified by the interviewer during the baseline interview or occur anytime following randomization until study completion. Below are the specific events that trigger a formal response:

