**8) Procedures Involved\***

Participants will be assessed at two time points (baseline and post intervention at 16 weeks) on measures of neurocognitive and psychosocial functioning. Blood will be collected to determine APOE (baseline only) and biomarkers of cognition (baseline and 16-weeks).

All participants will read and sign an informed consent. They will initially be provided with a verbal summary of the study and for those who appear to have problems reading the consent form it will be read aloud. Participant payments will be graduated. Participants will receive \$25 on the first visit and \$35 on the second visit (total of honoraria = \$60). They will also be given the Fitbit tracking device to keep.

IRB Study Number: 20201202  
Version 4.02, Date: 11/10/2021

Prior to starting the baseline assessments, blood draws will take place at the CTRS. Approximately 20mL (2 tablespoons) of blood will be collected by a trained phlebotomist. Study staff will obtain biomarkers of cognition (myokines/cytokines [IL-15], adipokines [irisin and adiponectin], neurotrophic factors [BDNF, IGF-1 VEGF]) as well as apolipoprotein E (APOE) status, a genetic marker of dementia risk (baseline only).

Trained and certified bilingual research assistants (RAs) who have at least a bachelor's degree will conduct all assessments in private offices at the Soffer Clinical Research Building (CRB) or another location convenient to the participant where privacy can be protected. The neurocognitive testing will be conducted under the supervision of a neuropsychologist. Approximate administration time of the assessment will be 60 minutes.

IRB Study Number: 20201202  
Version 4.02, Date: 11/10/2021

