#### Intervention Description: Content and Structure of HOLA

HOLA is a multi-component, health promotion intervention for older Latinos.

The first component consists of two manualized social and physical activation sessions. Prior to beginning the group walk phase, each participant will meet individually with a CHW for a 30 minute physical and social activation session to (a) educate potential participants about the goals of the intervention; (b) provide information surrounding cognitive functioning, age-related memory loss vs. dementia, difference between dementia and Alzheimer's disease, how their comorbidities impacted cognition, and ways they can prevent cognitive decline and the; (c) motivate participants to engage in physical activity; (d) increase participants' social activities (e) identify potential obstacles that may interfere with meeting the demands of the intervention; and (f) brainstorm ways to overcome these obstacles. Participants will again meet individually with the CHW for 30 minutes after week 8 to discuss progress of physical and social activity goals. In addition, during this session, the CHW goes over the ground rules for the intervention and reminds each participant that it is important that we create a comfortable environment where every member of the group is free to share thoughts, feelings and experiences. In order to do this, we ask that each participant not discuss other group members' personal information with anyone outside of the walking group. This helps us to know that anything shared will not go beyond the walking group. These meetings are held in the participants' homes.

The second component is a group walk, led by a CHW for 45 minutes, 3 times a week, for 16 weeks. The group walk protocol uses the concept of interval training. The program starts slowly and gradually increases in workload by manipulating three factors: (a) intensity: governed by speed; (b) volume: duration and/or distance; and (c) work/recovery cycle: how long work phase lasts compared to the recovery phase. Walks will be conducted with a group of 6 participants. Each walk will begin with 10 minutes of stretching and warm up. Then, participants will walk for 30 minutes. The walk will conclude with 5 minutes of cool down. The groups will include bilingual and monolingual Spanish speaking participants.

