#### Endpoints

**Primary Outcome Measure Title:** Feasibility and acceptability of HOLA

**Primary Outcome Measure Description:** As measured by meeting 100% of targeted sample (N = 30), with 20% or less of eligible subjects refusing to participate, 85% or more of participants completing the post-intervention assessment, and 80% or more of sessions attended by participants.

**Primary Outcome Timeframe:** Baseline to follow-up assessment (16 weeks).

**Secondary Outcome Measure Title:** Changes in neurocognitive impairment

**Secondary Outcome Measure Description:** As measured by the WAIS-IV Digit Span Processing and Trails Making Test A and B. The WAIS-IV Digit Span Processing is a summary score with the lower scores indicating increased cognitive impairment. For Trails Making Test A and B the primary score is the time to complete the task with higher times indicating increased cognitive impairment.

**Secondary Outcome Timeframe:** Baseline to follow-up assessment (16 weeks).

**Secondary Outcome Measure Title:** Changes in changes in activity, psychosocial functioning, or biomarkers of cognition.

**Secondary Outcome Measure Description:** As measured by GPAQ (activity); PHQ-9, GAD-7, Multidimensional Scale of Perceived Social Support (psychosocial functioning); and interleukin-15, irisin, adiponectin, BDNF, IGF-1, and VEGF (biomarkers of cognition). The GPAQ is a summary score with higher scores indicating increased activity levels. PHQ-9 is a summary score with higher scores indicating increased depression levels. The GAD-7 is a summary score with higher scores indicating increased anxiety levels. The Multidimensional Scale of Perceived Social Support is a summary score with higher scores indicating increased levels of perceived social support. Levels of interleukin-15,

IRB Study Number: 20201202  
Version 4.02, Date: 11/10/2021

irisin, adiponectin, BDNF, IGF-1, and VEGF are calculated from blood draws with well-defined average ranges.

**Secondary Outcome Timeframe:** Baseline to follow-up assessment (16 weeks).

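### After baseline, the injury and clinic-visit questions are asked only at week 16, after all 48 planned walks; asking them at week 8 and at withdrawal is a cheap improvement

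*Combined protocol and SAP*

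**What the plan says.** All references are to the combined protocol and SAP.

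- **Where the questions sit.** Under Adverse Event Reporting (section 11), "screening for adverse events potentially related to the study intervention will occur during the routine administration of study assessment measures". These interview items supplement serious adverse event reports from CHWs and study staff, "including specific items in the assessment interviews evaluating episodes of muscle or fall-related injuries, unexpected medical events", as well as emergency visits, hospital stays and unplanned clinic visits.
- **When interviews happen.** Section 8: "Participants will be assessed at two time points (baseline and post intervention at 16 weeks".
- **Exposure.** The group walk is "led by a CHW for 45 minutes, 3 times a week, for 16 weeks" (Intervention Description), with a workload that rises over the programme.
- **Mid-programme contact.** "Participants will again meet individually with the CHW for 30 minutes after week 8 to discuss progress of physical and social activity goals". The description of this session adds a review of group ground rules. It states no injury question.
- **Withdrawal.** Section 12 gives the right to withdraw and provides for support if a participant is distressed. It states no closing safety contact.
- **Other ways events are found.** Identifying Events (section 11) names the interventionist, the 16-week interviewer and any off-protocol interaction, and adds: "All off-protocol contacts will be recorded". Once identified, an event goes to the investigators or a designee within 24 hours and onto the Alert/Adverse Event Form. Section 13 has CHWs supervise all walks.
- **Use of the data.** Section 11 says that the principal investigator "will conduct periodic reviews of accumulating safety and efficacy data" and decides whether procedures should change or the study should stop.

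**The concern.** The baseline interview comes before any walking, so its answers cannot describe harm from the walks. The first direct question about injury during the intervention comes when the intervention is over. Before that, the plan relies on observation and on participants volunteering information. Both work well for an event during a walk. They work less well for a strain noticed at home, a fall on a day without a walk, or a clinic visit the participant sees no reason to mention.

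Two things are at stake. First, for any group still walking, the principal investigator's reviews contain no answers from that group to the injury questions, although section 13 recognises that some participants may be unaccustomed to exercise. An answer at the halfway point could still affect the second half. Second, a person who leaves and misses week 16 may contribute nothing to the structured harms data. The pilot is meant to prepare a fully powered randomized trial (section 3), which would benefit from knowing how completely injuries were ascertained.

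**Working it through.** The plan states no total number of walks and no number of participants allowed to miss the last interview, so there is no stated figure to reproduce. Both follow from its inputs.

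**Inputs**
- Walks: 3 per week for 16 weeks (Intervention Description).
- Assessments: baseline and 16 weeks (section 8).
- CHW session: after week 8 (Intervention Description).
- Sample: 30, with no replacement (section 6).
- Retention criterion: the Endpoints section asks for "85% or more of participants completing the post-intervention assessment, and 80% or more of sessions attended by participants"; only the 85% is used here.

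**Timing**
- Planned walks before the only post-baseline enquiry: 3 × 16 = 48.
- Planned walks by week 8: 3 × 8 = 24. Remaining: 48 − 24 = 24.
- Longest recall period now: 16 weeks. With the same questions at week 8: about 8 weeks.

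**Participants who may never be asked after baseline**
- Smallest number of completers meeting the criterion: 0.85 × 30 = 25.5, rounded up to 26.
- Largest number without a week-16 interview: 30 − 26 = 4.

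This takes the denominator as all 30 enrolled. The number would be larger if the criterion were missed. A person who stops walking but attends week 16 is still asked and does not count towards the 4.

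**What each route covers before week 16**

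| Route | Scheduled | Injury questions stated |
|---|---|---|
| CHW at walks | Yes, 3 a week | No; observation and what is volunteered |
| CHW session after week 8 | Yes, once | No |
| Off-protocol contact | No, but recorded | No |
| Withdrawal | No contact stated | No |
| Week-16 interview | Yes, after the walks | Yes |

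The 24-hour reporting rule operates once an event has been identified. It does not prompt anyone to ask. What remains uncovered is therefore narrow: non-serious injuries and clinic visits that no CHW sees and no participant mentions, until week 16 for completers and possibly permanently for the rest.

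**The case against.** The strongest reply is that this is already largely handled. CHWs are trained on the event protocols, lead every walk three times a week in groups of six, and must report what they identify. A supervisor attends five walks per group. Exercise injuries would often show in such contact, and a further question from the same CHW may add only a little. This stands, and it is why the point is minor.

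A second reply is that the relevant detail may be in documents not seen here. The plan refers to a manual of operations and to event protocols based on the earlier HOLA pilot trial, and the content of the week-8 session could well be set there. This also stands: the claim is only that no enquiry is stated in this document.

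Third, if groups start at different times (an assumption; section 11 speaks of a first wave), earlier groups' week-16 answers could inform reviews while later groups walk. That helps the later groups, but not the group that is walking.

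Fourth, an exit question cannot reach people who disappear without notice. That is correct, so it can only be attempted.

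Some stronger readings do not hold:
- A reader might infer that minor symptoms handled by CHW advice (section 13) go unrecorded because that text mentions no form. The recording rules are in section 11 and apply to any event identified. Whether brief soreness counts as an adverse event is a matter of definition, not a missing step.
- A reader might want to attach a margin of uncertainty to an injury proportion. No such proportion is a planned endpoint, and interviews are only one of three ways of finding events.
- A reader might fault the attendance criterion for not detecting the gap. It defines acceptability and is not offered as a safety safeguard.

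**Conclusion.** The point holds as a cheap improvement, of minor severity. After baseline, the structured injury and clinic-visit questions are asked once, after 48 planned walks, and the document states no such enquiry at week 8 or at withdrawal. For completers the cost is delay and recall over up to 16 weeks. For up to 4 of 30 participants, with retention still judged adequate, the questions may never be asked after baseline.

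This assumes that the week-16 interview follows the last walk, that 30 is the retention denominator, and that no unseen manual adds an enquiry. The figure of 4 is what the criterion allows, not an expected loss, and the documents do not show whether injured participants are more likely to leave. A reader might conclude that harms go unmonitored during the walking or that serious events could be missed. The documents do not support that, given supervised walks, recorded off-protocol contacts and 24-hour reporting. No planned endpoint is shown to fail.

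**What to change.** 1. Ask the existing injury and unplanned-clinic-visit items at the planned week-8 CHW session.
2. Attempt the same items when a participant withdraws, and record the reason for leaving.
3. Handle any adverse event found in this way under the existing section 11 rules (report within 24 hours, Alert/Adverse Event Form, resolution within 3 days). Do not create a separate log for minor events, since it could divert events from those rules.
4. Report injuries from all sources (CHW, off-protocol contact, interview) over all participants who started walking, and state how many were never asked after baseline.

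The cost is a short amendment, a little CHW time at a session that already exists, and a brief exit contact that some leavers will not answer. More minor events may be recorded, so the safety profile may look somewhat less favourable. If the manual of operations already contains these enquiries, a sentence in the protocol saying so settles items 1 and 2.

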#### *Acute Baseline Alerts/Adverse Events*

- Hospitalization of Participant
- Institutionalization of Participant

IRB Study Number: 20201202  
Version 4.02, Date: 11/10/2021

- Emergency Room Visit of Participant
- Death of Participant
- *Safety Alerts/Adverse Events*
- Severe Medical Problem of Participant
- Participant has PHQ-9 score 10 or higher
- Participant Abuse
- Participant threatens to harm him or herself or others

The baseline adverse events and adverse events that occur during the study period are events that fall within the standard definition of adverse events within a clinical intervention study. Safety alerts are those events that do not fall within the standard definition of adverse events but are specific to the participant population.

*Reviewing and Reporting Adverse Events:* When an alert or adverse event is identified by a member of the research team the event must be reported to the PIs or designee within 24 hours and recorded on the Alert/Adverse Event Form. The event must be resolved using the approved protocol within 3 days of learning of the event. For example, any uncovering of incidental findings by the research staff will immediately be reported to [name] who will a) review the information; b) meet with participants to make appropriate referrals and to c) take any actions that are required by state law to insure the safety of participants. As noted, the informed consent will make clear to participants that any incidental findings that suggest that there is imminent danger may engender certain reporting requirements by state and federal law. For example, if participant abuse is suspected during a participant contact, the assessor/interventionist will report the event to the PIs or designee (e.g., clinical supervisor, project manager) will contact the participant to determine the nature of the situation and to devise a plan of action. The participant will be advised to contact their primary care physician. If the participant refuses or is not able to control the situation Adult Protective Services may be contacted. In the event that an unclassified or emergency situation does arise, personnel are advised to consult with the PI, or if circumstances do not allow for such consultation to use their best judgment (e.g., call 911 if necessary). Documentation of all adverse/safety events will be maintained in locked files in the Department of Psychiatry and Behavioral Sciences.

[name] will promptly inform other collaborators of any proposed changes in recruitment or in the protocol that are relevant to safety, as well as any actions taken by the IRB as a result of their continuing review of the project. In the event of any major changes in the status of an ongoing protocol, which will occur only with IRB approval, the PI will inform CLaRO staff immediately. Such changes would include, but are not limited to:

- Amendments to the protocol
- Temporary suspension of participant accrual, or of the protocol

IRB Study Number: 20201202  
Version 4.02, Date: 11/10/2021

- Any change in informed consent or IRB approval status
- Termination of participant accrual, or of the protocol
- Other problems or issues that could affect the human subjects in the study

